1. SPECIFIC AIMS

Specific Aims. Following standards for developing and initially testing a behavioural intervention, this study will involve an iterative process of intervention development. The main aim is to conduct a pilot field test of a group based counselling intervention with HIV positive women in the perinatal period (N=40) as delivered by a lay counsellor (an individual who has completed the requirements to serve as an HIV counsellor, but who is not a clinical psychologist or social worker). The primary goal of the intervention is to improve the detection of perinatal depression and facilitate treatment, and increase adherence to antiretroviral therapy among HIV infected women during pregnancy and continued adherence during the postpartum period living in a resource limited setting; secondary outcomes will include reductions in stigma, increased social support, and improved adherence to other aspects of the postpartum PMTCT cascade, namely, contraception uptake. We have two hypotheses: *Hypothesis 1a: Women who participate in the intervention will have lower levels of depression and stigma, and increased levels of adherence to antiretroviral therapy, and other aspects of the postpartum PMTCT cascade (e.g., contraception uptake), and social support at the end of the intervention.* *Hypothesis 1b: The intervention will be both acceptable and feasible.*

Please note that this is a follow up (Phase II) study of a previous submission approved and completed under the same investigators (Clearance Certificate M110963).

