The intervention has been conceptualized as a group intervention as it has been proposed that interventions that make use of and foster social support may be helpful in decreasing social isolation and stigma among individuals living with HIV ¹⁰. In addition, interventions that target social networks and strengthen group ties have also been used to empower marginalized groups, and to effect health related behaviour change related to HIV prevention (e.g., ⁴²⁻⁴⁴). Lastly, group mental health interventions are cost-effective, which is of particular benefit in resource-limited settings ^{44,45}. The ideal number of participants per group will be approximately 2-10. In the event that enough participants cannot be recruited to participate in group-based sessions (i.e. due to scheduling concerns), individual sessions will be conducted. This data will be recorded and analysed as part of the feasibility and acceptability data.

Study procedures. After the informed consent document has been reviewed and signed, participants will be scheduled to complete a study intake assessment with the Project Manager or a Research Assistant. Once eligibility is determined, participants will be randomized to study condition. To allow an estimate of effect size for a larger trial, we will use a “treatment as usual” control group, and participants will be randomly assigned to a group. The treatment as usual group will consist of a referral to counselling services at PMMH, with the option of participating in the group sessions later (i.e. the next time the group is offered). Participants who will be postpartum by that time will be offered the option of attending a series of open problem-solving groups. With permission of the participants, we will send a referral letter documenting that criteria for depression have been met to a public health facility of the participants’ choosing to facilitate treatment for all participants who complete the baseline evaluation. Participants who do not wish to have a letter of this nature sent to a facility will be provided with a letter directly, if desired. We will also refer ALL participants who meet study inclusion criteria (or, those who do not meet criteria but could benefit from, or wish to be referred) to counselling services at PMMH,

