Participants will have as much time as they require to decide if they want to participate, even if this requires re-scheduling other portions of the visit to allow the participant more time to review the informed consent document. All procedures and protocols will have been approved by the Massachusetts General Hospital (MGH) institutional review board (IRBs) and the Wits University Human Research Ethics Committee and by PMMH and local and KwaZulu-Natal provincial health authorities before the inception of any study procedures.

Data analytic plan. All analyses conducted as part of this field test intervention are meant to lay the groundwork for future work, and it is not necessarily powered to detect statistically significant changes in depression, adherence, stigma, or social support. Because this is an

exploratory study, we will first examine the outcome variables continuously. We may determine cut-off scores that are appropriate to the sample and make clinical sense, and examine dichotomous outcomes (e.g., a reduction of 30-50% in depressive symptoms and/or the percentage of the sample scoring lower than $>/= 9$ on the Edinburgh Postnatal Depression Scale (EPDS) and achieving $\geq 90\%$ adherence) when assessing the effect of the intervention. Descriptive measures (such as mean, standard deviation, median, and range) will be used to summarize continuous patient characteristics (such as age, income) and categorical patient characteristics (such as ethnicity, employment status) will be summarized using frequencies and percent's. Descriptive data on the feasibility outcomes depicted in Figure 3 will be presented. With respect to qualitative exit interviews, data will be analysed using standard qualitative methodologies described by Miles and Huberman⁴⁶. After transcripts are translated to English, they will be reviewed for errors and omissions. NVivo software (version 9) will be used to organize data and to facilitate analyses. Two investigators, one of whom will be a South African study staff member (to ensure accurate interpretation), will independently review the transcripts in order to generate an overarching thematic framework for data interpretation, in which major and minor themes are identified.

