Social support	Modified version of the Duke-UNC Functional Social Support Questionnaire. ⁵² 10-item scale evaluating availability of emotional, informational, and tangible support. Items are rated on a 4-point Likert scale; number of persons providing support is also assessed.
Adherence to ARVs during pregnancy and PP (self-report and objective measure)	(1.) Adherence with ARV medications over the past month with three different response formats: (1) frequency, (2) percent, and (3) rating response. Category scores of 0, 20, 40, 60, 80, and 100, with 100 being the best adherence are calculated ⁵³ (2.) 30-day visual analogue scale (VAS) for overall adherence assessment for one month. Adherence is calculated as the % of doses taken over those prescribed and categorized into full, partial, and non-adherence. The VAS has been used in South Africa. ²³ MEMS caps will be brought to each session and each assessment and read for quantifiable adherence value (i.e. when the pill was opened every day).

Adherence to labour and delivery practices	Method of delivery (vaginal or Cesarean section); delivery in a healthcare setting (yes/no; ²¹)
Infant nevirapine administration	Select questions from the ACTG Paediatric International Adherence Questionnaire (NIAID Paediatric AIDS Clinical Trials Group). Assesses missed doses and reasons for missed doses. This measure has been used in South Africa.
Initiation of family planning methods	Initiation of family planning (yes/no); means of family planning (including intrauterine devices, oral and injectable hormonal contraception, implants, condoms). ^{54,55} These questions have been used in South Africa and Zambia.
Infant outcomes	HIV testing (yes/no); ¹¹ HIV status; gestational age; birth weight; mortality; birth date.
Breastfeeding	Assesses breastfeeding practices (breast, formula, mixed); reasons why participants may have chosen to opt out of breastfeeding or why they may have chosen to supplement breast milk.

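### Do the optional responder cut-offs, with no rule on when or how they are chosen, undermine the effect estimates?

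*Combined protocol and SAP*

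**What the plan says.** The quantitative plan is one paragraph, Data analytic plan, in section 3. It describes the analyses as groundwork for later work and the study as exploratory and not necessarily powered. On order, it states "we will first examine the outcome variables continuously". The cut-off clause follows: "We may determine cut-off scores that are appropriate to the sample and make clinical sense, and examine dichotomous outcomes". Its examples, introduced by e.g., begin "a reduction of 30-50% in depressive symptoms and/or the percentage of the sample scoring lower than" an EPDS value of 9, and end with at least 90% adherence. The dichotomies would serve in assessing the intervention's effect.

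Four other places bear on this:

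- Study procedures (section 3) gives the reason for the control arm: "To allow an estimate of effect size for a larger trial".
- Hypothesis 1a (section 1) places its outcomes, including depression and adherence, by time: "and social support at the end of the intervention".
- The primary goal (section 1) also reaches past birth: "increase adherence to antiretroviral therapy among HIV infected women during pregnancy and continued adherence during the postpartum period".
- Table 1 (section 4) lists several adherence measures. For self-report, "Category scores of 0, 20, 40, 60, 80, and 100, with 100 being the best adherence are calculated". There is also a 30-day visual analogue scale, and for the electronic caps "MEMS caps will be brought to each session and each assessment and read for quantifiable adherence value".

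**The concern.** Several things are left open: the percentage reduction within 30-50%, the and/or, the EPDS inequality (printed as lower than, followed by a greater-or-equal sign), the measure behind 90% adherence, and the visit. The adherence measures are not interchangeable. A single self-report category score moves in steps of 20, so it reaches 90% only at 100, whereas the visual analogue scale and the caps can take values between 90 and 100.

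Because the continuous results are looked at first and the cut-offs are to suit the sample, a reader can imagine the definition being chosen once the arms have been compared. The responder difference would then be too large on average, and always in the intervention's favour. If that figure were used to size the larger trial, the trial would be too small. A confidence interval calculated as if the definition had been fixed would not show the problem.

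**Working it through.** **No figure to reproduce.** The plan gives no significance level, power, SD, response rate or effect size. Only the 20 women per arm come from the document (Recruitment procedures). All EPDS distributions below are assumptions, used for scale.

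**Simulation.** Five scenarios, 20,000 trials each, integer EPDS 0-30, one follow-up visit. The four candidate definitions are EPDS below 9 and reductions of at least 30%, 40% and 50%. Three rules are compared:

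1. EPDS below 9, fixed in advance.
2. The definition with the largest difference favouring the intervention.
3. The definition whose pooled response rate, without arm labels, is nearest 50%.

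For rule 1 the sampling SD of the difference under no effect is √(2p(1−p)/20), with p the response rate. With p = 0.309 this is √(2 × 0.309 × 0.691 / 20) = 0.146, or 14.6 points.

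| Baseline mean/SD; follow-up mean/SD; correlation | Control below 9 (%) | SD, rule 1 | No effect, rule 2 | No effect, rule 3 | 0.4 SD shift, rule 2 |
|---|---|---|---|---|---|
| 15/4; 11/5; 0.5 | 30.9 | 14.6 | +8.2 | −0.4 | 25.4 |
| 15/5; 11/6; 0.4 | 33.8 | 15.0 | +8.2 | +0.1 | 24.5 |
| 16/4; 12/5; 0.5 | 24.2 | 13.5 | +8.3 | +0.1 | 25.0 |
| 18/5; 12/6; 0.5 | 27.9 | 14.2 | +8.8 | 0.0 | 25.4 |
| 18/4; 11/6; 0.4 | 33.9 | 15.0 | +8.3 | −0.2 | 24.5 |

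Under no effect the arms are exchangeable, so the true expectation for rules 1 and 3 is exactly zero; the small values for rule 3 are simulation noise. With a true shift of 0.4 SD, each definition on its own gives 14 to 18 points and the arm-blind pick gives 17 to 18. Rule 2 gives about 25, roughly 7 points above the largest single definition.

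**The EPDS slip.** Below 9 against 9 or below moves the control response rate by 6 to 7 points (for example 30.8% against 38.1% in the first scenario). That is a change of level. The same rule is applied to both arms, so it does not bias the comparison.

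**The continuous estimate.** It uses no cut-off. Its 95% confidence half-width at 20 per arm is t(38 df) × √(2/20) = 2.024 × 0.316 = 0.64 SD. Adjusting for a baseline correlation of 0.4 to 0.5 multiplies this by √(1−r²), giving 0.59 to 0.55 SD. This imprecision is the main limit on any effect size from the study, and the choice of cut-off does not alter it.

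**The case for a change.** The strongest case for a change is that exploratory status does not excuse a biased estimate when the stated purpose of the control arm is an effect size for later use. Selection bias runs one way, so it is not cancelled by being smaller than the sampling SD. The examples do not settle the definition, the plan contains no reporting rule that would expose selective choice, and a few sentences would remove the doubt without new data.

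Much of this stands as description: no passage fixes the timing, blinding, measure or visit of the dichotomies. What does not follow is that carrying out the plan gives a wrong answer.

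- The roughly 8 points require an analyst who picks on the between-arm result. The plan contains no such rule, and an arm-blind choice fits its words equally well.
- Suiting the sample can mean suiting this population. The depression example is a threshold on a scale that Table 1 describes as validated in South African perinatal women.
- Study procedures does not say that the effect size carried forward is a responder difference, and the analysis that comes first is continuous.
- The and/or can be read as a list of results to present, because its second half is a percentage of the sample and not a rule for one woman.
- On the visit, Hypothesis 1a already points to the end of the intervention, while the primary goal gives the postpartum visit its own purpose.
- The adherence measure is a matter of judgement. The caps are the objective measure, but they are uploaded at every intervention session as well as at assessments, so the intervention arm is read more often.

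**Conclusion.** The concern does not call for a change. The plan leaves an optional, secondary step without a written policy, and its EPDS inequality is a clerical slip that is sensibly read as below 9. An analyst would ordinarily report the continuous differences first, state the cut-offs used, and describe any that were derived from the data as such. The possible inflation of about 8 points rests on assumed EPDS distributions, one follow-up visit, and deliberate selection of the best of four definitions by arm. Without that selection the bias under no effect is zero, and the continuous estimates are untouched in every case. False-positive rates add nothing here, because the plan proposes no test. Anyone using this study to size a later trial should rely on the continuous results and their wide intervals, and treat any responder figure as descriptive.

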4. TABLES AND FIGURES

Figure 1: The PMTCT “cascade”

[figure not shown]

Figure 2: Conceptual model

[figure not shown]

Figure 3: Intervention feasibility

[figure not shown]

Figure 4: Participant Flow Chart

[figure not shown]

Table 1: List of proposed measures and assessments

Construct	Measurement tool and schedule
Sociodemographic and structural barriers	Age; ethnicity; educational level; employment status; occupation; income; distance to clinic; time spent travelling to clinic; mode of transportation to clinic.
Clinical information	Approximate due date, number of pregnancies, number of children, date of HIV diagnosis, number of children who are HIV positive
Partnership characteristics	Marital/partnership status; partner's HIV status; length of relationship with partner; if live with partner; disclosure to partner; partner involvement in pregnancy (yes/no).
HIV characteristics	CD4, viral load, year of diagnosis; disclosure status. World Health Organization staging classification for HIV stage, as available. Antiretroviral therapy regimen.
Pregnancy characteristics	Attitudes towards pregnancy and pregnancy intention as measured by the CDC PRAMS instrument; ^{33,47,48} parity. Instrument is scored using an accompanying variable codebook, with answers "Yes" scoring '1' and "No" scoring '0'. Number of antenatal care visits.
Depression	Diagnosis of current and past Major Depressive Disorder will be made using the Mini International Neuropsychiatric Interview (MINI), Major Depressive Episode Module. The Edinburgh Postnatal Depression Scale will also be utilized to measure depression at baseline, post treatment, and postpartum. This 10 item measure has been validated for broadly African and specifically South African populations specifically for perinatal and postpartum participants. ^{49,50}
Stigma	HIV/AIDS Stigma Instrument-People living with AIDS (HASI-P) has been developed and tested broadly in five African countries (including South Africa). The instrument was validated with a sample of 1,477 persons living with HIV/AIDS in those five countries. This is a large measure from which we are utilizing 3 sub-scales: negative self-perception items (n=5), social isolation (n=5), and verbal abuse (n=8). ⁵¹
Social support	Modified version of the Duke-UNC Functional Social Support Questionnaire. ⁵² 10-item scale evaluating availability of emotional, informational, and tangible support. Items are rated on a 4-point Likert scale; number of persons providing support is also assessed.
Adherence to ARVs during pregnancy and PP (self-report and objective measure)	(1.) Adherence with ARV medications over the past month with three different response formats: (1) frequency, (2) percent, and (3) rating response. Category scores of 0, 20, 40, 60, 80, and 100, with 100 being the best adherence are calculated ⁵³ (2.) 30-day visual analogue scale (VAS) for overall adherence assessment for one month. Adherence is calculated as the % of doses taken over those prescribed and categorized into full, partial, and non-adherence. The VAS has been used in South Africa. ²³ MEMS caps will be brought to each session and each assessment and read for quantifiable adherence value (i.e. when the pill was opened every day).

Adherence to labour and delivery practices	Method of delivery (vaginal or Cesarean section); delivery in a healthcare setting (yes/no; ²¹)
Infant nevirapine administration	Select questions from the ACTG Paediatric International Adherence Questionnaire (NIAID Paediatric AIDS Clinical Trials Group). Assesses missed doses and reasons for missed doses. This measure has been used in South Africa.
Initiation of family planning methods	Initiation of family planning (yes/no); means of family planning (including intrauterine devices, oral and injectable hormonal contraception, implants, condoms). ^{54,55} These questions have been used in South Africa and Zambia.
Infant outcomes	HIV testing (yes/no); ¹¹ HIV status; gestational age; birth weight; mortality; birth date.
Breastfeeding	Assesses breastfeeding practices (breast, formula, mixed); reasons why participants may have chosen to opt out of breastfeeding or why they may have chosen to supplement breast milk.

